Increases in major adverse cardiovascular events (MACE), including myocardial infarction, cerebrovascular accident, and cardiovascular death, reported initially with anti-IL-12/23 agents such as ustekinumab, have not been observed in longer-term studies with risankizumab. While the likelihood of increased MACE is small, all suspected cardiovascular or cerebrovascular events (serious or nonserious) observed in this study will be adjudicated by an independent Cardiovascular Adjudication Committee (CAC). The committee will remain blinded to treatment allocation (Section 6.2).

Local reactions to subcutaneously (SC) administered biologic therapies are usually limited to redness, swelling, or induration at the injection site. Manifestations of systemic hypersensitivity reactions include anaphylaxis, pruritus, hypotension, and respiratory distress. Both local and systemic hypersensitivity reactions are readily detectable, transient in nature, and manageable with standard medical treatment. Subjects will be closely monitored during study drug administration while at the site and be given instructions regarding management of signs and symptoms of anaphylaxis to be followed during home dosing visits. An independent Anaphylaxis Adjudication Committee (AAC) will adjudicate observed systemic hypersensitivity and anaphylactic events. The AAC will remain blinded to treatment allocation (Section 6.3).

In conclusion, the benefit-risk profile of risankizumab is considered appropriate for this stage of clinical development.²⁵ Based on data from the integrated safety analyses, risankizumab is safe and well tolerated and demonstrates a favorable benefit-risk profile.

For further details, please see findings from completed studies, including safety data, in the current risankizumab Investigator Brochure.¹⁷

In view of the coronavirus disease of 2019 (COVID-19) pandemic, the benefit-risk profile of various immunomodulatory therapies on COVID-19 is being evaluated based on real world data and clinical trial data. At this time, the effects of risankizumab on the course of COVID-19 are not well defined.

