Randomization/drug assignment		✓						
Study drug administration		×	×	×	✓	×		
Dispense urine pregnancy tests for women of child-bearing potential (for potential virtual visits due to COVID-19)		~						

Activity	Screening	Baseline	Week 4	Week 16	Week 28	Week 40	Week 52/Premature Discontinuation	
			Day 29	Day 113	Day 197	Day 281	Day 365	20 Week Safety
Visit window	Day -35 to -1	Day 1	± 3	days		± 7 da	ys	F/U Call
Dispense Subject Dosing Diary (for potential virtual visits due to COVID-19)		~						
Self-Injection Training		×		✓				
Hypersensitivity Training		 Image: A second s		×				
Hypersensitivity monitoring		✓	~	✓	~	✓		

BL = Baseline; BSA = Body surface area; CBC = Complete blood count; COVID-19 = coronavirus disease – 2019; DLQI = Dermatology Life Quality Index; ECG = Electrocardiogram; FSH = Follicle-stimulating hormone; F/U = Follow-up; HBV = Hepatitis B virus; HCV = Hepatitis C virus; HIV = Human immunodeficiency virus; IGRA = Interferon gamma release assay; PASI = Psoriasis Area and Severity Index; PD = Premature Discontinuation; PGA-SP = Patient Global Assessment of Skin Pain; PPD = Purified protein derivative; PPASI = Palmoplantar Psoriasis Area and Severity Index; ppIGA = Palmoplantar Investigator's Global Assessment; PSS = Psoriatic Symptom Scale; SARS-CoV-2 = Severe acute respiratory syndrome coronavirus 2; sPGA = static Physician's Global Assessment; TB = Tuberculosis

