9.0 Efficacy Analyses

9.1 General Considerations

All efficacy analyses will be conducted among the ITT Population. All statistical tests will be performed at a 2-sided alpha level of 0.05.

The Primary Analysis will be conducted after all continuing subjects complete Week 16 and all data pertaining to Period A are cleaned. This will be the only and final analysis for efficacy in Period A. Study sites and subjects will remain blinded to their initial treatment assignment for the duration of the entire study.

For categorical endpoints, comparisons will be made between risankizumab and placebo using the Cochran-Mantel-Haenszel (CMH) test, adjusting for the actual values of stratification factors (Baseline ppIGA and Baseline BSA categories). In case of any stratum with zero subject in either treatment group, no stratification factor will be controlled. Non-responder imputation (NRI) incorporating multiple imputation (MI) to handle missing data due to COVID-19 (NRI-C) will be the primary approach to handle missing values.

For continuous endpoints, comparisons will be made between risankizumab and placebo based on the fixed term of treatment from a Mixed-effect Model Repeat Measurement (MMRM) model including the Baseline value and observed measurements at all post-baseline visits, adjusting for the fixed effects of treatment, actual values of stratification factors, visit and treatment-by-visit interaction as covariates. The MMRM will be the primary approach to handle missing values.

"Baseline" refers to the last non-missing observation on or before the date of the first administration of study drug or the date of randomization if no study drug is administered. For variables where the assessment time is collected on the ePRO device, the baseline measurement must be prior to the time of the first administration of study drug.

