10.3 Analysis of Laboratory Data

Data collected from central and local laboratories, including additional laboratory testing due to an SAE, will be used in all analyses, except for Baseline derivation where SAE-triggered laboratory assessments on or before the first dose of study drug will be excluded. The clinical laboratory tests defined in the protocol operations manual (e.g., hematology and clinical chemistry) will be summarized.

Mean change from Baseline to each applicable post-baseline visit will be summarized for selected laboratory variables. The following descriptive statistics will be presented by treatment groups: number of observations, Baseline mean, visit mean, mean change from Baseline and its standard error, and the 95% confidence interval of the mean change from Baseline.

In addition, laboratory parameters will be tabulated using shift tables from Baseline to minimum and maximum values in each period (Period A and Period B), categorized by the toxicity grade according to NCI CTCAE Version 4.03³ of the laboratory used for each sample. A similar shift table will also be provided to summarize shifts from Baseline to the final post-baseline value in each period.

Laboratory abnormalities meeting CTC criteria grade 3 and 4 at least once in each period will be summarized.

Laboratory abnormalities will be evaluated based on Potentially Clinically Important (PCI) criteria ([Appendix C](#)). For each laboratory PCI criterion, the number and percentage of subjects who have a laboratory value meeting the criteria at least once in each period will be summarized. Listings will be provided to summarize subject-level laboratory data for subjects meeting PCI criteria.

In addition, the frequencies and percentages of subjects with post baseline liver specific function test values in ALT/SGPT, AST/SGOT, alkaline phosphatase, and total bilirubin that meet the following criteria will be summarized by treatment groups:

- $ALT > 3.0 \times ULN$
- $ALT > 5.0 \times ULN$
- $ALT > 10.0 \times ULN$
- $ALT > 20.0 \times ULN$
- $AST > 3.0 \times ULN$
- $AST > 5.0 \times ULN$
- $AST > 10.0 \times ULN$
- $AST > 20.0 \times ULN$
- Alkaline phosphatase $> 1.5 \times ULN$
- Total bilirubin $> 1.5 \times ULN$
- Total bilirubin $> 2.0 \times ULN$
- ALT and/or AST $> 3.0 \times ULN$ and Total bilirubin $> 1.5 \times ULN$
- ALT and/or AST $> 3.0 \times ULN$ and Total bilirubin $> 2.0 \times ULN$
- ALT $> 3 \times ULN$ and Total bilirubin $> 1.5 \times ULN$

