10.4 Analysis of Vital Signs

Vital sign measurements of systolic and diastolic blood pressure will be summarized.

Change from baseline to each applicable post-baseline visit will be summarized for each vital sign variable. The following descriptive statistics will be presented by treatment groups: number of observations, Baseline mean, visit mean, mean change from Baseline and its standard error, and the 95% confidence interval of the mean change from Baseline.

Vital sign variables will be evaluated based on potentially clinically important (PCI) criteria ([Appendix D](#)). For each vital sign PCI criterion, the number and percentage of subjects who have a vital sign value meeting the criteria at least once in each period will be summarized. Listings will be provided to summarize subject-level vital sign data for subjects meeting PCI criteria.

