Appendix D. Criteria for Potentially Clinically Important Vital Sign Values

Vital Signs Variables	Criterion	Definition of Potentially Clinically Important
Systolic Blood Pressure (mmHg)	Low	Value \leq 90 mmHg and decrease \geq 20 mmHg from Baseline
	High	Value \geq 160 mmHg and increase \geq 20 mmHg from Baseline
Diastolic Blood Pressure (mmHg)	Low	Value \leq 50 mmHg and decrease \geq 10 mmHg from Baseline
	High	Value \geq 100 mmHg and increase \geq 10 mmHg from Baseline

Appendix E. Non-Responder Imputation Incorporating Multiple Imputation to Handle Missing Data Due to COVID-19 Pandemic for Dichotomized Outcome Variables

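### The Baseline rule in SAP 9.1 works by calendar date, so a blood pressure or laboratory value recorded after the Day 1 injection could become Baseline (minor; the frequency may be zero)

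*SAP*

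**What the plan says.** SAP 9.1 gives the only general definition: Baseline "refers to the last non-missing observation on or before the date of the first administration of study drug", or the randomization date if no drug is given. It then adds a stricter rule for one class of data: "For variables where the assessment time is collected on the ePRO device, the baseline measurement must be prior to the time" of first dosing. Vital signs and laboratory values are not in that class.

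The definition sits in the efficacy section, and Section 10 supplies no other. SAP 10.3 adds one safety exception. Central and local laboratory data enter all analyses "except for Baseline derivation where SAE-triggered laboratory assessments on or before the first dose of study drug will be excluded". SAP 10.4 has no equivalent for vital signs.

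Several safety outputs use Baseline:
- SAP 10.4: "Change from baseline to each applicable post-baseline visit will be summarized for each vital sign variable".
- SAP Appendix D ("Criteria for Potentially Clinically Important Vital Sign Values"): each blood pressure criterion needs both an absolute threshold and a change from Baseline.
- SAP 10.3: mean change and shift tables for laboratory variables.
- SAP Appendix C: a laboratory PCI finding needs a worse grade than at Baseline.

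On timing, Protocol 5.7 has site staff give the first dose at the Baseline visit. The activity schedule (Protocol Appendix D) marks vital signs and chemistry/hematology once each on Day 1. It also lists "Hypersensitivity monitoring" that day. Only the urine pregnancy row is marked as pre-dose.

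**The concern.** A value taken an hour after the injection satisfies a rule based on the date. Being the last such value, it also displaces the pre-dose value. The SAP evidently accepts that a reference value should precede exposure, because it imposes that condition on ePRO variables and screens out some laboratory draws. Blood pressure has no such protection, nor does a laboratory value prompted by a non-serious event.

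A repeat measurement on Day 1 is plausible. Protocol 2.2 says "Subjects will be closely monitored during study drug administration while at the site" and lists hypotension among the manifestations of systemic hypersensitivity, so blood pressure is a natural thing to measure again. At stake are the PCI counts for blood pressure and laboratory variables, and the change and shift summaries for the subjects concerned.

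**Working it through.** There is no planned figure to reproduce, because the point concerns a derivation rule and not a sample size or an error rate. The check applies the rule to assumed readings.

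**Inputs from the documents**
- Baseline rule: SAP 9.1, last value by date.
- Systolic low PCI: value at or below 90 mmHg and a fall of at least 20 (SAP Appendix D).
- Systolic high PCI: value at or above 160 mmHg and a rise of at least 20 (SAP Appendix D).
- Planned arm size: 84 (SAP 2.4).

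**Assumed inputs:** all systolic readings below. The documents give none.

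Change = later value - Baseline. Under the date rule Baseline is the Day 1 post-dose reading. Under a time rule it is the pre-dose reading.

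| Case | Pre-dose | Day 1 post-dose | Week 4 | Date rule | Time rule |
|---|---|---|---|---|---|
| a | 125 | 88 | 124 | Baseline 88; Day 1 reading not flagged; Week 4 change 124 - 88 = +36 | Day 1 fall 125 - 88 = 37 and value at or below 90: low PCI; Week 4 change 124 - 125 = -1 |
| b | 135 | 165 | 165 | Week 4 change 165 - 165 = 0; no flag | Week 4 change 165 - 135 = +30; high PCI |
| c | 150 | 138 | 160 | Week 4 change 160 - 138 = +22; high PCI | Week 4 change 160 - 150 = +10; no flag |

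Cases a and b lose a flag and case c gains one, so the error can run in either direction.

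**Effect on an arm mean.** In case a the Week 4 change is wrong by 36 - (-1) = 37 mmHg. If all 84 subjects in the arm contribute, one such subject moves the arm's mean change by 37/84 = 0.44 mmHg.

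**Laboratory values.** The mechanism is the same: a worse grade recorded post-dose on Day 1 becomes the Baseline grade, and a later value of that grade no longer counts. The scope is narrower. SAP 10.3 keeps SAE-triggered draws out of Baseline. The samples named in Protocol 6.3 after a suspected systemic reaction (tryptase, histamine, drug concentration, anti-drug and neutralizing antibodies) are not PCI variables in Tables C-1 or C-2. What remains is a same-day repeat hematology or chemistry panel for a non-serious reason.

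**Frequency.** With one Day 1 value taken before dosing, both rules give the same Baseline. The number affected runs from zero up to every subject with a recorded same-day post-dose value. The documents do not allow a narrower estimate.

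**The case against.** The strongest objection is that the triggering data are not in the plan. Vital signs and the hematology and chemistry panel are scheduled once on Day 1, with no post-dose row. Monitoring for hypersensitivity does not mean that a numerical blood pressure is taken and entered as an analysable record. Procedure details are deferred to the Operations Manual, which was not available here. It may already place Day 1 assessments before the injection. This stands, and it is why the point is conditional and the frequency may be zero. It does not repair the rule, which would still admit an unscheduled later reading.

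A reader might infer the stronger claim that post-dose values do replace pre-dose values and so hide acute reactions. The documents do not support it. Adverse events with onset on the first dose date are treatment-emergent (SAP 10.2.1). Suspected systemic hypersensitivity needs a supplemental form (Protocol 6.1, Table 3), and suspected anaphylactic reactions go to blinded adjudication (Protocol 6.3). Hypersensitivity and adjudicated anaphylaxis are areas of safety interest (SAP Appendix B). None of these uses a Baseline value. What can be lost is a PCI flag, not the clinical event.

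That does not make the PCI table redundant. Under Protocol 6.1 a vital-sign or laboratory change is an adverse event only if it leads to discontinuation from the study, needs medical intervention, or is judged to be one by the investigator. A transient, untreated fall may meet none of these, and the PCI count is then where it would appear.

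It can also be said that a date rule is sensible where no time is collected. That is fair, and the fix needs a fallback for that case.

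**Conclusion.** The point holds as a gap in the wording of SAP 9.1. A recorded same-day post-dose blood pressure, or a hematology or chemistry value not triggered by an SAE, would become Baseline. It could then remove or create a PCI flag and would distort that subject's change from Baseline.

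The size is small. It is confined to subjects with a second recorded value on Day 1, and there may be none. In the assumed example, each such subject moves an 84-subject arm mean by 0.44 mmHg. The vital-sign summaries are descriptive, with no hypothesis test.

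The primary endpoint, the power and the type I error control are unaffected. Baseline ppIGA is needed for eligibility and for stratified randomization, so it is scored before the first dose.

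The conclusion assumes that the definition in 9.1 also governs Section 10, since no other is given, and that unscheduled Day 1 values enter the analysis data if recorded. Priority is minor: a free improvement, not a threat to the trial's conclusions.

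**What to change.** In SAP 9.1:
1. Define Baseline for all variables, stating that this includes those in Section 10, as the last non-missing value before the time of first study drug administration. This extends to all data the condition now set for ePRO variables, that "the baseline measurement must be prior to the time of the first administration of study drug".
2. Where no assessment time is recorded, use the scheduled Baseline-visit record and exclude unscheduled records from the same day. If the Operations Manual places Day 1 vital signs and blood draws before the injection, say so in the SAP, because the fallback relies on that order.

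In SAP 10.3 and 10.4, treat any Day 1 value known to be post-dose as post-baseline, so that it can count toward the PCI tables. Keep the existing exclusion of SAE-triggered laboratory values from Baseline.

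The cost is one sentence in 9.1, a clause in 10.3 and 10.4, and one programming condition. No new data are needed: recorded times are used where they exist, and the fallback covers the rest.

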5.7 Study Drug

AbbVie will provide study drug for risankizumab or matching placebo. AbbVie-provided study drug should not be substituted or alternately sourced unless otherwise directed by AbbVie. Information about the study drug and placebo used in this study is presented in Table 2.

During Period A (Double-Blind Period), study site staff will administer study drug subcutaneously (risankizumab 150 mg or matching placebo in a pre-filled syringe [PFS]) at Baseline and Week 4 visits. Subjects will be trained by site staff on self-injection at the Baseline visit to proactively be prepared for at-home dosing by the subject or caregiver at Weeks 4, 28, and 40, should the need for a virtual visit arise due to COVID-19-related restrictions. Subjects may be retrained on self-injection at the Week 16 visit.

During Period B (Open-Label Period), study site staff will administer risankizumab as a 150 mg SC dose $(1 \times 150 \text{ mg PFS})$ at Week 16, Week 28, and Week 40 visits.

Only subjects who self-administer study drug at home due to COVID-related visit modifications (e.g., virtual visit) will record the self-administered dosing in a subject dosing diary.

Route of **Study Drug Dosage Form** Strength Administration Manufacturer Risankizumab (ABBV-066) Solution for 150 mg Active, SC injection AbbVie Biotechnology injection in PFS 150 mg/mL Ltd., Barceloneta, Puerto Rico Placebo for Risankizumab Solution for AbbVie Deutschland Not applicable SC injection (ABBV-066) injection in PFS GmbH & Co. KG,

Table 2. **Description of Study Drug and Placebo**

PFS = pre-filled syringe; SC = subcutaneous

Blinded risankizumab or placebo and open-label risankizumab will be packaged in quantities sufficient to accommodate study design. Each kit will be labeled per local requirements and this label must remain affixed to the kit. Upon receipt, study drug must be kept protected from light in the original packaging,

Ludwigshafen, Germany

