4.0 Analysis Populations

The Intent-to-Treat (ITT) Population includes all randomized subjects. The ITT Population will be used for all efficacy analyses. Subjects who are randomized to placebo in Period A and do not continue into Period B will be excluded from the analysis in Period B.

The following populations will be used for the safety analysis:

- The Safety Population in Period A (Safety_A) is defined as all subjects who are randomized and received at least 1 dose of study drug in Period A.
- The Safety Population in Period B (Safety_B) is defined as all subjects who received at least 1 dose of study drug in Period B.

- The All Risankizumab Treated (ALL_RZB) Population is defined as subjects who received at least 1 study drug of risankizumab. This population will be used to provide a comprehensive summary of key safety variables.

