10.0 Safety Analyses

10.1 General Considerations

Safety analyses will include adverse events, laboratory, and vital sign measurements.

Safety data will be summarized among the Safety_A and Safety_B populations by treatment groups. For the safety analysis, subjects are analyzed based on the actual treatment group, determined by the first dose of study drug that the subject received.

The overview of TEAEs, areas of safety interest (ASIs), and potentially clinically important (PCI) findings in laboratory variables and vital sign variables will be summarized among the ALL_RZB Population.

Missing safety data will not be imputed.

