10.2.1 Treatment-Emergent Adverse Events

Treatment-emergent adverse events (TEAEs) for each safety period are defined as follows:

Period A: A TEAE in Period A is defined as any event with an onset date on or after the first dose date of study drug in Period A and within 140 days after the last dose date of study drug in Period A, as long as it does not exceed the first dose date in Period B.

Period B: A TEAE in Period B is defined as any event with an onset date on or after the first dose date of study drug in Period B and within the minimum of (140 days after the last dose date of study drug in Period B, and the end of study date).

The All-Risankizumab Treated Period: A TEAE is defined as any event with an onset date on or after the first dose date of risankizumab and within the minimum of (140 days after the last dose date of risankizumab, and the end of study date).

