Appendix C. Potentially Clinically Important Criteria for Safety Endpoints

The criteria for Potentially Clinically Important (PCI) laboratory findings are described in Table C-1 and Table C-2.

Table C-1. Criteria for Potentially Clinically Important Hematology Values

Hematology Variables	Units	Definition of Potentially Clinically Important: NCI CTCAE (Version 4) Grade 3 or Greater
		Very Low
Hemoglobin	g/dL	< 8.0
Platelets count	$10^9/L$	< 50.0
WBC count	$10^9/L$	< 2.0
Neutrophils	$10^9/L$	< 1.0
Lymphocytes	$10^9/L$	< 0.5

Note: A post-baseline grade must be more extreme than the baseline grade to be considered a potentially clinically important finding.

Table C-2. Criteria for Potentially Clinically Important Chemistry Values

Chemistry Variables	Units	Definition of Potentially Clinically Important: NCI CTCAE (Version 4) Grade 3 or Greater	
		Very Low	Very High
Total Bilirubin	mcmol/L		$> 3.0 \times \text{ULN}$
ALP	U/L		$> 5.0 \times \text{ULN}$
SGOT/AST	U/L		$> 5.0 \times \text{ULN}$
SGPT/ALT	U/L		$> 5.0 \times \text{ULN}$
Albumin	g/L	< 20	
Glucose	mmol/L	< 2.2	> 13.9
Triglycerides	mmol/L		> 5.7
Creatinine	mcmol/L		$> 3.0 \times \text{ULN}$ or $> 3.0 \times \text{baseline}$
Sodium	mmol/L	< 130	> 155
Potassium	mmol/L	< 3.0	> 6.0
Calcium	mmol/L	< 1.75	> 3.1
CPK	U/L		$> 5.0 \times \text{ULN}$
Total Cholesterol	mmol/L		> 10.34
GGT			$> 5.0 \times \text{ULN}$

Note: A post-baseline grade must be more extreme than the baseline grade to be considered a potentially clinically important finding.

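### Potentially clinically important findings in the all-risankizumab population are judged against a pre-placebo Day 1 value for placebo-randomised subjects, although that population's other safety measures start at the first risankizumab dose

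*SAP*

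**What the plan says.** - **Baseline.** SAP 9.1 sets it as "the last non-missing observation on or before the date of the first administration of study drug", with the randomisation date as fallback for subjects never dosed. The SAP gives no other definition. SAP 10.3 works from the same anchor for laboratory values, referring to "Baseline derivation where SAE-triggered laboratory assessments on or before the first dose of study drug will be excluded".
- **Study drug.** Protocol 5.7 states: "AbbVie will provide study drug for risankizumab or matching placebo". For a subject randomised to placebo, the first administration is therefore the Day 1 placebo injection.
- **ALL_RZB.** SAP 4.0 has this population "defined as subjects who received at least 1 study drug of risankizumab". Under SAP 2.2 every continuing subject starts open-label risankizumab at Week 16, so it includes placebo-randomised subjects who enter Period B.
- **Time origin in ALL_RZB.** Treatment duration (SAP 6.0), treatment-emergent adverse events (SAP 10.2.1) and patient-years (SAP 10.2.4) all begin at the first risankizumab dose. An adverse event counts if it is "any event with an onset date on or after the first dose date of risankizumab", up to the end of the follow-up window.
- **Outputs in ALL_RZB.** SAP 10.1 lists the adverse event overview, the areas of safety interest, and then: "potentially clinically important (PCI) findings in laboratory variables and vital sign variables will be summarized among the ALL_RZB Population".
- **PCI rules.** For laboratory tests, Appendix C requires: "A post-baseline grade must be more extreme than the baseline grade to be considered a potentially clinically important finding". Creatinine can also qualify by exceeding three times baseline. In Appendix D every blood-pressure criterion combines an absolute limit with a minimum change from Baseline.

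**The concern.** The SAP distinguishes first study drug from first risankizumab wherever ALL_RZB needs it, except in Baseline. Two outputs for the same people therefore run on different origins. An adverse event that began on placebo is left out of ALL_RZB, but a laboratory or blood-pressure change that began on placebo can enter it as a PCI finding. The reverse can also happen: a subject who was abnormal on Day 1, normal at Week 16 and abnormal again on risankizumab may not be counted.

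There is a related gap in wording. SAP 10.3 and 10.4 count PCI findings per period, but do not tie the ALL_RZB count expressly to values recorded after the first risankizumab dose.

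At stake is the readability of one descriptive table. ALL_RZB is the population meant to give the overall picture of safety on risankizumab, and its PCI table is its only laboratory and vital-sign content.

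**Working it through.** The plan states no figure on this point, so there is none to reproduce. The check traces the Baseline rule through the ALL_RZB outputs.

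**1. Who carries the Day 1 reference.** The planned size is 84 per group (SAP 2.4). If every placebo subject enters Period B, the share is 84 / (84 + 84) = 50%. The documents give no dropout rate. Assuming 10% or 20% of placebo subjects do not continue:
- 10%: 84 × 0.90 = 75.6, and 75.6 / (84 + 75.6) = 47%
- 20%: 84 × 0.80 = 67.2, and 67.2 / (84 + 67.2) = 44%

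**2. Which ALL_RZB outputs use Baseline.**

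| Output (SAP 10.1) | Time origin | Uses Baseline? |
|---|---|---|
| Adverse event overview | First risankizumab dose | No |
| Areas of safety interest | First risankizumab dose | No |
| PCI laboratory findings | Not stated separately | Yes (Appendix C) |
| PCI vital signs | Not stated separately | Yes (Appendix D) |

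**3. Blood pressure.** The high systolic rule in Appendix D flags a value of at least 160 mmHg that is at least 20 mmHg above Baseline. Two invented placebo-randomised subjects, judged at Week 52:

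| Day 1 / Week 16 / Week 52 | Change from Day 1 | Flagged under SAP? | Change from Week 16 | Flagged from first risankizumab? |
|---|---|---|---|---|
| 138 / 160 / 160 | 160 − 138 = +22 | Yes | 160 − 160 = 0 | No |
| 165 / 135 / 165 | 165 − 165 = 0 | No | 165 − 135 = +30 | Yes |

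The first is flagged although nothing changed on risankizumab. The second is missed although pressure rose 30 mmHg on risankizumab. The error can go either way.

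**4. Laboratory tests.** PCI means Grade 3 or worse and worse than the baseline grade. Apart from the creatinine ratio, the choice of Baseline matters only if the subject is already at Grade 3 or worse on Day 1 or at Week 16. For several tests, the entry limits at Screening (Protocol 5.1) are far from the PCI limits (Appendix C):

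| Test | Entry limit | PCI limit |
|---|---|---|
| ALT, AST | ≤ 2 × ULN | > 5 × ULN |
| Hemoglobin (g/dL) | ≥ 10 | < 8 |
| Platelets (10⁹/L) | ≥ 100 | < 50 |
| White cells (10⁹/L) | ≥ 3.0 | < 2.0 |
| Neutrophils (10⁹/L) | ≥ 1.5 | < 1.0 |

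For these, a Grade 3 value on Day 1 is nearly excluded. After Baseline, routine chemistry and hematology are scheduled only at Week 16 and at Week 52 or premature discontinuation (Protocol Appendix D). A carried-over finding would normally have to last 52 − 16 = 36 weeks. Glucose, triglycerides, creatine kinase and blood pressure have no numeric entry limit, so both routes stay open for them.

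**5. Size.** The documents give no rate of new, persisting PCI findings on placebo. As a conversion only, each 1% of placebo-randomised subjects affected is 84 × 0.01 = 0.84 subjects, or 0.84 / 168 = 0.5% of ALL_RZB.

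**The case against.** The strongest reply is that the SAP is silent rather than wrong. The Baseline sentence sits in the efficacy section, and the clause in SAP 10.3 concerns excluding SAE-triggered samples, so neither was written as an ALL_RZB rule. The SAP also draws on a Product Safety SAP that is not among the documents and may hold a convention. This stands only in part. SAP 10.3 does use the first-study-drug anchor for its laboratory Baseline. If SAP 9.1 did not reach safety data, the vital-sign criteria would have no Baseline at all. A convention held elsewhere would still need a cross-reference.

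The second reply is that the effect is small and partly visible already. That stands. The laboratory route is narrow for tests with entry limits. Confirmed ALT or AST above 5 × ULN for more than 2 weeks is a withdrawal criterion (Protocol 5.5), which limits carry-over. Subject-level listings are planned for everyone who meets a PCI criterion (SAP 10.3 and 10.4). A placebo-period finding also appears under placebo in the Period A table. The listings let a reader trace a misplaced finding, but they do not correct the count, and they do not show a subject whose change was masked.

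**Conclusion.** The inconsistency is real and narrow. Followed as written, the plan judges ALL_RZB PCI findings in placebo-randomised subjects, at most 84 of 168, against a value taken before placebo, while the rest of ALL_RZB starts at risankizumab. Counts can be too high or too low. The effect is confined to descriptive PCI counts, mainly blood pressure and laboratory tests without entry limits. Its size cannot be estimated from the documents and may be near zero for tests with entry limits. The 84 is a ceiling that assumes no loss before Week 16, and the systolic values are illustrations.

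A reader might infer more, and the documents do not support it:
- **That half of ALL_RZB safety has the wrong reference.** Adverse events and areas of safety interest do not use Baseline, and SAP 10.1 plans no shift or mean-change tables for ALL_RZB.
- **That Period B tables attribute placebo-period change to risankizumab.** They are shown by treatment group, fixed by the first study drug received, so placebo-first subjects form their own column. Their change from Day 1 mixes both periods, but it is a legitimate summary if labelled.
- **That a few percent of ALL_RZB would be misattributed.** No figure in the documents supports any such rate.

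Period A, efficacy and type I error are untouched.

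**What to change.** Add to SAP 10.1: for PCI summaries in ALL_RZB, Baseline is the latest non-missing value up to the first risankizumab dose, and only values after that dose count as post-baseline. For placebo-randomised subjects this is normally the Week 16 value, taken before that visit's injection. For subjects randomised to risankizumab nothing changes.

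Keep the Day 1 Baseline for Period A and efficacy. Period B tables by treatment group may keep it too, with a footnote saying that change is measured from Day 1, so that both columns share one reference.

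The cost is one sentence and one extra derived baseline flag. Chemistry, hematology and vital signs are already scheduled at Week 16 (Protocol Appendix D), so no new data are needed.
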